### **6.2.2 Equivalency Checks**

PRIDE will ensure that randomization is stratified by substance use (including marijuana). Further, we will monitor randomization to ensure that condition is not associated with characteristics that would require adjustment in proposed analyses.

### **6.2.3 Equivalency Tests**

A series of bivariate analyses will be conducted to examine between condition differences at baseline and evaluate the success of randomization procedures. We will utilize chi square tests of independence, t-tests, ANOVA and Spearman's rho correlations as appropriate to examine whether intervention conditions differed significantly with respect to key demographic variables and outcome variables at baseline. In the event that significant baseline differences are observed, these demographic factors will be incorporated into subsequent outcome analyses.

### **6.2.4 Power Analysis**

We will enroll a total of 260 substance-using MYMSM (130 per condition) engaged in HIV risk behavior; this will be 1.8 times more participants than in the original efficacy trial, providing adequate power to detect differences in this real-world setting. We conducted a series of simulations using SAS 9.2 PROC GLIMMIX to examine power to detect intervention effects on primary outcomes. In each simulation, 500 draws were requested and effects averaged across samples assuming 260 enrolled participants with retention of 85% at 12-month follow-up (n = 221). All models included a random effect for counselor assuming approximately 12 peer counselors across sites by the end of the study. Consistent with existing CDC and NYCDOH data on 12month STI incidence among MYMSM, we allowed the proportion of positive diagnoses in the eTAU/YMHP groups to vary between 0.15/0.04 and 0.20/0.07, respectively, and found 81.0% average power (i.e.,  $1 - \beta$ ) to detect statistically significant differences at  $\alpha = 0.05$  (i.e., 95% confidence). Utilizing the effect sizes found within the original YMHP efficacy trial (that utilized an intensive attention-control group), we set the proportion of individuals in the eTAU group who engaged in CAS at follow-up to 0.50 and to 0.30 in the YMHP group and found 85.4% power to detect significant differences at  $\alpha = 0.05$ , suggesting effects of this magnitude or larger will be sufficiently powered. Finally, examining substance use, assuming that the proportion of individuals in the eTAU group who persist in substance use over time is .80, we will have power to detect proportions of .62 or smaller in the YMHP group as statistically significant with power of 83.0% or greater at  $\alpha = 0.05$ .

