### **6.2 Quantitative Analysis Plan**

Primary Outcome Measures:

- Days of Illicit Drug Use (past 30 days)
- Days of Marijuana Use (past 30 days)
- Condomless Anal Sex Acts (past 30 days)

Secondary Outcome Measure:

- Days of Alcohol Use (past 30 days)

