#### **Phase 2**

Qualitative analysis: Interviews will be transcribed prior to data analysis. The team will use NVivo to conduct thematic content analyses to identify implementation barriers and facilitators. Using constant comparison analytic methods, a preliminary codebook will be developed both deductively and inductively. Research Scientist and another member of the team will code each interview. Divergent coding will be discussed, decision trails will be created at key decision-making junctures, and consensus-building strategies will resolve discrepancies. Findings will be used to inform revisions of the YMHP implementation package.

Statistical analysis: The primary hypothesis is that participants randomized to receive YMHP will demonstrate significant reductions in sexual risk behavior and associated health outcomes as well as substance use frequency and severity when compared to those who randomized to eTAU. We will utilize stratified block randomization with substance use and interventionist as the strata in order to assign all participants to a condition.

A series of bivariate analyses within SPSS (version 27) evaluated the success of randomization and the presence of differential attrition. With respect to randomization,  $\chi^2$  tests of independence evaluated between-condition differences across demographic characteristics (race and ethnicity, sexual identity, relationship status, education, income, and age). Where cell sizes for categorical variables were too small ( $n < 5$ ) to permit chi-square tests, we utilized a Fisher's exact test. The generalized linear model function in SPSS – which permits the specification of Poisson and negative binomial outcome variable distributions – was used to evaluate between group differences in baseline frequency of primary (marijuana use days, other illicit drug use instances, and CAS with male partners) and secondary (alcohol use days) outcomes. Likewise,  $\chi^2$  analyses were used to evaluate whether the probability of retention at each follow-up was associated with site, condition or categorical demographic factors; meanwhile, the generalized linear model component of SPSS was used to test whether retention at follow-up was associated with baseline primary or secondary outcome frequency.

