Outcome analyses were conducted using piece-wise latent growth curve (LGC) models following procedures outlined by Chou et al., (Chou et al., 2010) and used previously in similar studies (Flora, 2008; Kohli et al., 2013; Li et al., 2001; Naar-King et al., 2009; Naar et al., 2020). Growth trajectories over-time following the delivery of an intervention may be characterized by a large initial response followed by a more sustained trajectory with a less dramatic slope. Piece-wise LGC models quantify this kind of trajectory through the use of two slopes. Slope 1 quantifies the change from baseline to the immediate post-test (3-month follow-up). Meanwhile, Slope 2 quantifies the trajectory over the post-intervention follow-up period.

All primary (marijuana use, other illicit drug use, and CAS with male partners) and secondary (alcohol use) outcomes were modeled as negative binomial distributions. All models were estimated using full-information maximum likelihood estimation in MPlus Version 8.0. This permitted the retention of all randomized cases consistent with a true intent to treat paradigm. Many commonly used indices of model fit are not available for growth models with count-distributed outcomes (i.e., root-mean square error of approximation (RMSEA)  $\leq 0.05$ , Tucker-Lewis fit index (TLI)  $> 0.95$ , and comparative fit index (CFI)  $> 0.95$ ). Model fit was therefore

evaluated using a robust log-likelihood  $\chi^2$  test (Satorra & Bentler, 2001) comparing the log-likelihood of the specified model to a null-model – in which all structural coefficients associated with the regression of latent growth factors on condition and site were constrained to be zero.

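### The power figures in section 6.2.4 are for three yes/no comparisons, but the primary outcomes are 30-day counts with no power stated; STI has a power figure but no specified analysis

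*Combined protocol and SAP*

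**What the plan says.** Section 6.2.4 (Power Analysis) says: "We conducted a series of simulations using SAS 9.2 PROC GLIMMIX to examine power to detect intervention effects on primary outcomes". It then gives three scenarios, all binary:

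- **STI diagnosis:** "we allowed the proportion of positive diagnoses in the eTAU/YMHP groups to vary between 0.15/0.04 and 0.20/0.07", with 81.0% average power.
- **Any CAS:** "the proportion of individuals in the eTAU group who engaged in CAS at follow-up to 0.50 and to 0.30 in the YMHP group", with 85.4% power.
- **Persistence in substance use:** 0.80 under eTAU against 0.62 or lower under YMHP, with power of at least 83.0%.

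The sample behind all three is described as "assuming 260 enrolled participants with retention of 85% at 12-month follow-up (n = 221". The Duration paragraph of the Study Abstract notes that the 12-month assessment was removed in May 2020, although sections 4.2 to 4.4 and 4.6 still list it.

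Section 6.2 names three primary outcomes: days of illicit drug use, days of marijuana use, and "Condomless Anal Sex Acts (past 30 days", all over 30 days. Days of alcohol use is secondary. Under Phase 2, the primary and secondary "outcomes were modeled as negative binomial distributions" in piece-wise latent growth curves estimated by full-information maximum likelihood. The text adds: "This permitted the retention of all randomized cases consistent with a true intent to treat paradigm".

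Laboratory STI testing is scheduled at baseline and at the 3- and 9-month follow-ups (section 4.2). It is not an outcome in section 6.2 or among the primary outcomes in section 4.8, and sections 6.2 to 6.2.3 contain no STI analysis. The nearest wording is the hypothesis of "significant reductions in sexual risk behavior and associated health outcomes as well as substance use frequency and severity".

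**The concern.** A reader will take 81-85% as the power of the primary analysis. Those figures belong to a different endpoint type, a different model and a different sample from the analysis described. There is therefore no stated power or detectable effect against which to read a null result from the count models. One substance-use proportion also stands in for two separate primary outcomes. Illicit-drug days and marijuana days may have quite different means and zero fractions, not least because randomisation has a marijuana-only stratum.

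STI has the reverse problem. A power figure implies that it will be tested, yet no definition, time point or model is given. It matters because every outcome listed in section 6.2 is self-reported by participants who know whether they had four sessions or one. Whether a laboratory result will stand beside them should not be left open.

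**Working it through.** **1. Reproduce the plan's figures.** Inputs from section 6.2.4: 260 × 0.85 = 221, or 110.5 per arm; alpha 0.05, taken as two-sided (an assumption, since sidedness is not stated). For the pooled two-proportion test, with p̄ = (p0 + p1)/2:

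power = Φ{ (|p0 − p1| − 1.96·√[2p̄(1 − p̄)/n]) / √[(p0(1 − p0) + p1(1 − p1))/n] }

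For CAS, the standard errors are 0.0659 (null) and 0.0645 (alternative), so power = Φ[(0.20 − 1.96 × 0.0659)/0.0645] = 86.4%.

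| Comparison | p0 / p1 | Recomputed | Stated |
|---|---|---|---|
| STI, lower | 0.15 / 0.04 | 80.1% | 81.0% (average) |
| STI, upper | 0.20 / 0.07 | 81.2% | |
| Any CAS | 0.50 / 0.30 | 86.4% | 85.4% |
| Substance use | 0.80 / 0.62 | 84.3% | 83.0% |

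The stated figures come from 500 draws, so their simulation error is about √(0.83 × 0.17/500) = 1.7 points, and the gaps are within it. One-sided tests (88-92%) match none of the figures. They are therefore two-sided binary comparisons in 221 people, and they are arithmetically sound.

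**2. Compare with the planned analysis.**

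| | Section 6.2.4 | Section 6.2, Phase 2 |
|---|---|---|
| Outcome type | proportion | 30-day count |
| Substance use | one undivided proportion | illicit-drug days and marijuana days, separately |
| Model | GLIMMIX with counselor random effect | negative binomial piece-wise growth curve |
| Sample | 221 at 12 months | all randomised cases, all visits |
| STI | powered | no outcome, no analysis |

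**3. Can the binary figures stand in for the counts?** The documents give no mean, dispersion or rate ratio, so this step is illustrative, for CAS only. Assumptions: a non-zero 30-day count is what section 6.2.4 means by engaging in CAS; a common negative binomial dispersion k of 0.5 to 3; the effect acts through the mean; one time point. Since P(0) = (1 + kμ)^(−1/k),

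μ = [(1 − p)^(−k) − 1]/k,  RR = μ1/μ0,  SE² = (1/μ0 + k)/n + (1/μ1 + k)/n per arm,  power = Φ(|log RR|/SE − 1.96).

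Example, k = 1, 0.50/0.30, n = 110.5: μ0 = 1.00, μ1 = 0.429, RR = 0.429, SE = 0.220, power = Φ(0.847/0.220 − 1.96) = 97.1%.

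The 24% lower likelihood of CAS that section 1.4 reports for the original trial can be read two ways. As a risk ratio it gives 0.50 × 0.76 = 0.38. As an odds ratio it gives 0.76/1.76 = 0.432. Both rows use n = 229 (260 × 0.88, the 9-month retention in section 4.4).

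| CAS effect | n | RR, k = 0.5 to 3 | Power, k = 0.5 / 1 / 2 / 3 |
|---|---|---|---|
| 0.50 / 0.30 (section 6.2.4) | 221 | 0.47 to 0.27 | 95.2 / 97.1 / 99.1 / 99.8% |
| 0.50 / 0.38 (24% as risk ratio) | 229 | 0.65 to 0.46 | 62 / 68 / 79 / 87% |
| 0.50 / 0.432 (24% as odds ratio) | 229 | 0.79 to 0.64 | 26 / 29 / 37 / 44% |

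The answer depends far more on the effect assumed than on the 8-person difference in n: the planned effect at n = 229 still gives 95.8-99.8%.

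No such conversion is offered for substance use. The 0.80/0.62 pair describes neither illicit-drug days nor marijuana days.

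**The case against.** The strongest reply is that dichotomising usually costs power, so binary figures are a conservative stand-in. For the planned CAS effect that is what step 3 shows: 95-99.8% against 85.4% stated. The growth model also uses repeated visits and everyone randomised, which may raise power further. And the Phase 2 text is written largely in the past tense, so restating power now changes neither sample size nor analysis; a null result is better read from the confidence interval of the rate ratio. Much of this stands, and it makes the power half of the point mainly a matter of correct labelling. But the plan does not offer the binary figures as a conservative proxy. The reassurance also does not carry over to the smaller effect in section 1.4, and nothing comparable can be said for the two drug-use counts.

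A reader might infer that the trial is underpowered for its primary outcomes. The documents do not support that. The lower ranges rest on one-time-point assumptions and on how a single sentence in section 1.4 is read, and a larger effect against a single eTAU session is possible. Nor does the removed 12-month visit make n = 221 the wrong size for the primary model, since no single visit's n is the basis of a model that keeps all randomised cases. For STI, a reader might infer that a planned outcome was dropped. The documents show only that its status was never settled; the phrase about associated health outcomes could have been meant to include it.

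**Conclusion.** The point holds, and it should be fixed. Section 6.2.4 attaches 81.0%, 85.4% and 83.0% to the primary outcomes, but these are powers of binary comparisons that the plan does not run. None of the three primary counts has a stated mean, dispersion, rate ratio or power, and the two drug-use counts are not powered separately. The mismatch and the missing STI analysis follow from the text alone.

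Its size in power terms cannot be fixed from the documents. For CAS acts the illustration runs from 26% to 99.8%, depending on dispersion (0.5 to 3, assumed), on the effect (0.50/0.30 or the 24% in section 1.4) and on whether that 24% is a risk ratio or an odds ratio. These are not powers of the growth model. The conclusion is that power for the primary analysis is undemonstrated, not that it is low.

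**What to change.** **Power (section 6.2.4).** State that the three figures apply to binary comparisons and not to the primary count models. Give the power, or the detectable rate ratio, for each of the three primary counts under the planned growth model, using the visits actually retained and all randomised participants, with the assumed mean, dispersion and rate ratio written out. Explain how the 0.50/0.30 assumption relates to the 24% in section 1.4. If analysis is already done, label the result retrospective and base it on planning assumptions, not on observed effects.

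**STI.** Choose one of two courses. Either remove the STI power figure and state that STI is not an outcome, or list laboratory STI as a dated secondary outcome, marked post hoc if outcome data had been seen. In the second case the definition must:

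- handle missed tests (section 4.2 moves a missed test to the next assessment, and after 9 months there is none if the 12-month visit is gone);
- handle participants with past syphilis, who are generally not retested (section 4.5.1);
- not treat two test points as equal to the 12-month incidence behind the power figure.

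The model should adjust for baseline STI and both randomisation strata (substance use and interventionist).

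**Cost.** Wording and one simulation, plus one further model on data already collected if STI is kept. No new visits or participants. The stated power may change.

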## **6.3 Cost-Effectiveness Analysis Plan**

In order to enhance the likelihood of uptake if effective, the AC will conduct analyses to assess the cost-effectiveness of two delivery models of YMHP in reducing sexual risk and substance use utilizing CDC's guidelines for cost effectiveness analysis on HIV infections averted.

Interventions such as YMHP are intended to prevent infection in HIV-negative YMSM. Therefore, YMHP can be evaluated to determine the number of infections prevented that would have otherwise occurred had it not been provided at our sites. We will model our analyses based on the framework for a cost-utility analysis of addiction treatment, with emphasis on the Holtgrave and Kelly model [61-65] because they also examined a behavioral health intervention to prevent HIV infection [66].

Our economic analysis will have two components: 1) a cost analysis of the YMHP intervention; and 2) an incremental cost effectiveness analysis that compares the value of clinic-delivery of YMHP over remote delivery.

### **6.3.1 YMHP Program Cost Analysis**

In order to enhance the likelihood of uptake if effective, we will conduct analyses to assess the cost-effectiveness of YMHP in reducing substance use and sexual risk behaviors compared to eTAU utilizing CDC's guidelines for cost effectiveness analysis on HIV infections averted [67]. Our economic analysis will have two components: 1) a cost analysis of the YMHP intervention; and 2) an incremental cost effectiveness analysis that compares the value of YMHP to eTAU.

We will use a modification of The Drug Abuse Treatment Cost Analysis Program (DATCAP) [63, 68] plus study contact and expenditure records, to estimate the cost of the YMHP and eTAU conditions. Using both conditions will increase the stability of the measurements. The DATCAP is a standardized data collection instrument that estimates the economic cost of addiction treatment programs. Administration of the DATCAP is generally a collaborative effort involving an economist ([name]) and various members of the intervention staff (Health Educators, administrators, accounting/finance personnel, etc.). The DATCAP organizes program resources into personnel, buildings and facilities, supplies and materials, and miscellaneous resources. Client case flow data are incorporated to determine the average annual cost per client for each service type. Other useful computations include weekly cost per client, average cost per intervention episode (based on length of stay in the program), and marginal cost per contact [69-71][76-78][71-73][71-73][70-72][69-71].

We will first estimate the marginal costs of delivering YMHP as compared to eTAU. Using data from the modified DATCAP and study contact and expenditure records, key statistics from the cost evaluation will include total annual economic cost for the program, weekly economic cost per client, and total economic cost per intervention [episode/session]. To highlight the relative contribution of the various cost components and necessary future budgeting, we will also perform a descriptive analysis of the cost accounted for by resource category.

The mean aggregate cost of the interventions will be used as inputs in the cost effectiveness model. The number of HIV infections averted due to the YMHP intervention will be estimated

using the results from the clinical trial combined with published HIV infection risk rates for the specific risk behaviors. These data will be combined in a mathematical model structured as a decision tree with a long-term follow-up component using a Markov model structure. This combined structure will best capture the complexity of the clinical trial data and well as the uncertainty embedded in the HIV risk prediction equations, and minimize the number of assumptions required for the cost effectiveness estimate.

Cost-effectiveness will be modeled for YMHP as compared to eTAU and for the differences in CAS and predicted through Markov modeling for 5 and 10 years and over a lifetime using varying assumptions about decay of the effect of the intervention over time. Modeling will be performed from the perspectives of 1) a third party payer, 2) the medical care system, and 3) society.

**Model Structure.** We will use an HIV mathematical model with clinical findings from the study, YMHP cost data, clinical and epidemiological data from published studies, and cost data from archival databases. The model uses a combined decision tree and Markov approach to estimate treatment effects of CAS on HIV infection rates. Crystal Ball Monte Carlo estimation software will be used to simulate outcomes for a patient cohort under varying assumptions about the distribution of the data for the model parameters.

**Model Parameters:** Critical data in the model will come from the clinical parameters (substance use and CAS) and the study intervention cost data. Incidence of HIV infection projections after the end of the study will be based on analysis of epidemiologic data from large patient cohorts or on reported values in the literature. Quality of life weights are based on literature reports and archival data. Direct intervention costs for YMHP and eTAU will be estimated as described above. Cost of medical care will be based on Medicaid data; other costs will be based on the literature or archival data. The effects of different costing perspectives will be assessed. Both cost and years of life will be discounted by 3% when cost effectiveness is examined.

**Model Outputs:** The model will estimate 5-year and 10-year flow of fund differences to example individuals, Medicaid, private insurers, and other payers under specific assumptions, as well as overall cost effectiveness and cost utility estimates. Differences in expected population survival, quality of life, and costs attributable to YMHP will also be reported. We will perform sensitivity analysis using a Monte Carlo simulation.

**Limitations:** We will minimize the effects of data variation by using several data sources, bootstrapping, and sensitivity analysis with a Monte Carlo approach to examine the effect of variations in parameters and differences in distributional assumptions in our model.

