## 2.1 Specific Aims

**Aim 1:** Adapt the YMHP intervention for delivery in CBOs by Health Educators. We will conduct focus groups with site staff to obtain further input on the best ways to implement YMHP in CBO settings to maximize feasibility, acceptability, and sustainability.

**Aim 2:** Test the effectiveness of the YMHP intervention delivered in two CBOs situated in high HIV incidence neighborhoods in NYC using a CET. We will test YMHP – an efficacious, MI-based intervention – versus enhanced treatment as usual (eTAU) condition (standard HIV C&T and prevention services with information about PrEP) in reducing substance use and CAS among HIV-negative MYMSM.

**Aim 3:** Assess the cost-effectiveness of YMHP. In order to enhance the likelihood of uptake if effective, we will conduct analyses to assess the cost-effectiveness of YMHP compared to eTAU.

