## **5.0 INTERVENTION PROCEDURES**

### **5.1 Intervention Design and Procedures**

YMHP is a CDC Best Evidence Intervention [59] that utilizes MI and personalized feedback to reduce CAS and substance use among YMSM. The YMHP intervention will be delivered by MI-trained Health Educators employed at each of the two CBOs. Participants will be randomized to receive either the intervention or an eTAU session with the Health Educator. The intervention condition involves completion of 4 YMHP sessions and the delivery of PrEP information and navigation services to interested participants. The control condition involves the completion of a single session eTAU that reviews the array of services offered by the CBO and also provides an overview of PrEP and PrEP-related services.

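### The Aim 3 model in section 6.3.1 carries HIV infections averted through CAS and names no PrEP input, so any difference between arms in PrEP coverage would be missed

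*Combined protocol and SAP*

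**What the plan says.** **Economic model (section 6.3.1).** The target quantity is infections prevented: "The number of HIV infections averted due to the YMHP intervention will be estimated", and this is to be done "using the results from the clinical trial combined with published HIV infection risk rates for the specific risk behaviors". Under Model Structure: "The model uses a combined decision tree and Markov approach to estimate treatment effects of CAS on HIV infection rates". Under Model Parameters: "Critical data in the model will come from the clinical parameters (substance use and CAS) and the study intervention cost data". The contrast carried into the five-year, ten-year and lifetime projections is the YMHP versus eTAU difference in CAS. For later years: "Incidence of HIV infection projections after the end of the study will be based on analysis of epidemiologic data from large patient cohorts", or on values reported in the literature. Sections 6.3, 6.3.1 and 6.3.2 do not mention PrEP uptake, adherence, effectiveness or cost.

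**PrEP content of the arms.** Section 5.1 defines the YMHP condition as "completion of 4 YMHP sessions and the delivery of PrEP information and navigation services to interested participants". The single control session "also provides an overview of PrEP and PrEP-related services", and Aim 2 (section 2.1) describes eTAU as standard counselling and testing and "prevention services with information about PrEP". In section 5.1.1, Session One gives basic facts on PrEP efficacy, and Session Three allows for a navigation plan where appropriate. Sessions Two and Four do not mention PrEP.

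**PrEP data.** Section 3.1 excludes men currently taking Truvada as PrEP. The schedule of measures in section 4.8 collects the PrEP cascade at baseline, immediate post-test and follow-up, and PrEP adherence at immediate post-test and follow-up.

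**The concern.** Aim 3 values the whole YMHP package against eTAU. Part of that package is help in obtaining PrEP, which prevents HIV without changing the number of CAS acts. A model that reads the trial's effect on infection from CAS alone cannot register this route. If CAS is more frequent among men on PrEP, such a model could even count uptake as added risk.

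Because current PrEP users are excluded at entry, PrEP use after enrolment can be compared between randomised arms. The trial therefore holds the data for a PrEP input, and the plan does not say whether they will be used. Two analysts following section 6.3.1 could reach different answers for the same trial. At stake are infections averted and the cost-effectiveness estimates built on them.

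**Working it through.** The plan states no figure for infections averted, so there is nothing to reproduce. The point rests on the text; the arithmetic shows only when the gap matters.

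**Text, side by side.**
- Named trial inputs: substance use, CAS, intervention cost. Only CAS has a stated link to HIV infection.
- Intervention content: PrEP information in both arms; navigation named only for YMHP, and only for interested participants.
- Data collected: PrEP cascade and adherence, both arms, after baseline.
- Stated link between those data and the model: none.

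**Illustration.** Let R be the ratio of CAS (YMHP/eTAU), e the effectiveness of PrEP, and cT and cY the shares of CAS acts that occur on PrEP in eTAU and YMHP. With infections proportional to CAS × (1 − e·c):

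- named inputs only: fraction averted = 1 − R
- with PrEP: fraction averted = 1 − R × (1 − e·cY)/(1 − e·cT)

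Inputs from the documents: R = 0.76 (section 1.4, 24% less likely to engage in CAS) and R = 0.30/0.50 = 0.60 (section 6.2.4). R = 1 is added as the case of no CAS effect. Both documented ratios describe engaging in any CAS, whereas the section 6.2 outcome is a count of acts, and the 24% comes from a comparison with content-matched education, not eTAU. They are stand-ins.

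Assumed, because the documents give no values: e from 0.5 to 0.9, and all coverage figures. Coverage equals uptake only if CAS is equally frequent on and off PrEP.

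Example: R = 0.76, e = 0.5, cT = 0.10, cY = 0.25 gives 1 − 0.76 × 0.875/0.95 = 30.0%.

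| Coverage eTAU / YMHP | R = 0.76 | R = 0.60 | R = 1 |
|---|---|---|---|
| Named inputs only | 24.0% | 40.0% | 0% |
| 0.15 / 0.15 | 24.0% | 40.0% | 0% |
| 0.05 / 0.15 | 27.9% to 31.2% | 43.1% to 45.7% | 5.1% to 9.4% |
| 0.10 / 0.25 | 30.0% to 35.3% | 44.7% to 48.9% | 7.9% to 14.8% |
| 0.25 / 0.10 | 17.5% to 10.8% | 34.9% to 29.5% | −8.6% to −17.4% |

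Each range runs from e = 0.5 to e = 0.9; a negative value means more infections under YMHP.

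**Equal coverage.** The fraction averted does not change. The count could still change: if the published risk rates describe men not on PrEP, it scales by (1 − e·c), which at c = 0.15 is 0.925 (e = 0.5) to 0.865 (e = 0.9).

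**Uptake is not coverage.** Suppose uptake is 10% in eTAU with CAS equally frequent on and off PrEP (coverage 10%), and 15% in YMHP with CAS half as frequent on PrEP. YMHP coverage is 0.15 × 0.5/(0.85 + 0.15 × 0.5) = 0.075/0.925 = 8.1%. Uptake is higher in YMHP, yet coverage is lower.

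**The case against.** The best defence is that section 6.3.1 is an outline. It calls substance use and CAS critical data, not a closed list, and it also draws on trial results and published clinical and epidemiological data in general terms. Medical costs are described just as generically, so PrEP cost is no more unnamed than any other medical cost. Staff time spent on navigation can be captured through the cost instrument and the resource records in section 6.3.2. The cited modelling framework and guidance, which are not available here, may say how PrEP is to be handled.

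Most of this stands. A reader might infer that the plan excludes PrEP; it does not, it leaves PrEP unspecified. A reader might also infer that CAS acts on PrEP are counted at full risk; that holds only if the published risk and incidence inputs are free of PrEP use, which the documents do not say. Nor do they support a picture of navigation delivered throughout four sessions: the session outlines place a navigation plan in Session Three only, conditionally.

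What does not stand is the idea that general wording or the Monte Carlo analysis closes the gap. Varying parameters does not add a missing pathway. Published inputs that average over PrEP users apply the same factor to both arms and still miss a difference between them.

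**Conclusion.** The gap is real and confined to Aim 3. As written, the model takes the trial's effect on HIV through CAS and does not say how PrEP enters. If the share of CAS acts covered by effective PrEP differs by arm, infections averted and cost-effectiveness are misstated.

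The size is unknown. At the largest assumed coverage gap (15 percentage points), the illustrated fraction averted shifts by 4.7 to 14.8 points upward or 5.1 to 17.4 points downward, and those values follow wholly from assumed coverage and effectiveness.

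It is tempting to conclude that the model understates the benefit of YMHP. The documents do not support that: they report no uptake by arm, direction depends on coverage and not on uptake alone, and PrEP cost can move the cost-effectiveness result the other way.

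Section 4.8 lists PrEP uptake under a primary-outcome heading, while section 6.2 names no PrEP outcome. A reader might infer that a primary outcome was dropped. The same heading also covers a cannabis-perceptions measure collected only at baseline, and Aim 2 names no PrEP outcome, so this looks like a labelling mismatch and adds no weight here. The Aim 2 comparisons are unaffected.

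**What to change.** In section 6.3.1:

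- State how PrEP enters the model. Use uptake and adherence by arm from the survey data already scheduled in section 4.8, with published PrEP effectiveness and PrEP cost.
- Give sensitivity ranges that include equal uptake and different CAS levels on and off PrEP.
- Check whether the external risk and incidence inputs already reflect PrEP use, so that it is not counted twice.
- Sections 6.2 and 6.2.4 mix tenses, and the outcome analyses in 6.2 are reported as done. If the addition is made after results were known, label it post hoc.

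As housekeeping, align the section 4.8 heading with the outcome list in section 6.2, either by relabelling it or by listing PrEP uptake by condition as a secondary, descriptive outcome.

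The cost is a few sentences, one comparison on data in hand and a few more model inputs. The downsides are that PrEP use is self-reported, the schedule of measures does not show the recall periods of the PrEP items, and effectiveness and cost must come from the literature. The CAS outcome and the Aim 2 analysis stay as they are.
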